7.6 Serious Adverse Events and Recording and Reporting

1) Definition of SAE

SAE refers to medical events that occur during clinical trials that require hospitalization or prolonged hospitalization, disability, affect work ability, endanger life or death, or cause congenital malformations.

Including the following unexpected medical events: events leading to death; Life threatening events (defined as the risk of immediate death for the subject at the time of the event); Events that require hospitalization or prolonged hospitalization; Events that can lead to permanent or severe disability/functional impairment/affect work ability; Congenital abnormalities or birth defects; Other important medical events (defined as events that endanger the subjects or require intervention to prevent any of the above situations from occurring).

2) Disease progression

Disease progression is defined as the deterioration of the subject's condition caused by the primary tumor targeted by the research treatment. Including advances in imaging and clinical symptoms and signs. The emergence of new metastases relative to the primary tumor, or the progression of

existing metastases, are considered as disease progression. Events that pose a threat to life due to symptoms and signs of disease progression, require hospitalization or prolonged hospitalization, or result in permanent or severe disability/functional impairment/impact on work ability, congenital abnormalities, or birth defects, are not included in accelerated reporting as SAEs. Deaths caused by symptoms and signs of disease progression are reported as SAEs at an accelerated rate.

3) Perform other anti-tumor treatments

The AE records start from the signing of the informed consent form and continue until 90 days after the last use of the study drug. Within 90 days after the last administration, if the subject begins to use other tumor drugs and experiences serious adverse events, a report is required.

4) Hospitalization

Adverse events leading to hospitalization or prolonged hospital stay in clinical studies should be considered as SAEs. Any first-time hospitalization by a medical institution meets this standard. Hospitalization does not include the following situations: rehabilitation institutions; Sanatorium; Routine emergency room admission; Same day surgery (such as outpatient/same day/non bedridden surgery); Hospitalization or prolonged hospital stay that is not related to the worsening of AE is not itself an SAE. For example, being admitted to the hospital due to an existing illness, without any new adverse events or worsening of the existing illness (such as in order to check for laboratory abnormalities that have persisted since before the experiment); Hospitalization due to management reasons (such as annual routine physical examinations); Hospitalization as specified in the trial protocol during clinical trials (such as operating according to the requirements of the trial protocol); Elective hospitalization unrelated to the worsening of adverse events (such as elective surgery); The scheduled treatment or surgical procedure should be recorded in the entire trial protocol and/or individual baseline data of the subjects.

Diagnostic or therapeutic invasive procedures (such as surgery) and non-invasive procedures should not be reported as adverse events (AEs). However, if the disease condition that led to this procedure meets the definition of AE, it should be reported. For example, acute appendicitis that occurred during the AE reporting period should be reported as an AE, and appendectomy performed as a result should be recorded as the treatment method for that AE.

5) SAE's reporting system

The reporting period for SAE should start from the signing of the informed consent form by the subjects and continue until 90 calendar days (including 90 days) after the last use of the study drug. If a serious adverse event (SAE) occurs, whether it is the first report or follow-up report, the researcher must immediately fill out the "New Drug Clinical Research Serious Adverse Event Report Form", sign and date it, and report it to the relevant provincial, autonomous region, or municipality drug regulatory department, NMPA (via EMS), health administrative department (via fax to the Medical Administration Bureau), notify the applicant (via email), and promptly report to the ethics committee within 24 hours of the researcher's knowledge.

SAE occurring 90 days after the last use of the study drug is generally not reported unless suspected to be related to the study drug. SAE should provide detailed records of symptoms, severity, correlation with the investigational drug, occurrence time, treatment time, measures taken, follow-up time and methods, as well as outcomes. If researchers believe that a certain SAE is not related to the investigational drug but potentially related to the study conditions (such as termination of the original treatment or comorbidities during the trial), this relationship should be detailed in the narrative section of the SAE report form. If the intensity of an ongoing SAE or its relationship with the investigational drug changes, a follow-up report should be submitted immediately.

6) Follow up of SAE

All SAEs should be followed up until disappearance, remission to baseline level or \leq level 1, and stability.

Researchers should be followed up until the end of AE, stable status, reasonable explanation, loss to follow-up, or death; Follow up information should be provided promptly according to the requirements of the sponsor.

If there are no specific requirements in the protocol, AE/SAE collection and follow-up usually begin after the subjects sign the informed consent form, and each AE/SAE must be followed up during the study period; At the end of the study, the collection and follow-up principles for AE/SAE that occurred after the final treatment of the subjects can refer to the following table:

Classification, collection, recording, and follow-up

All SAEs should be followed up until disappearance, remission to baseline level or \leq level 1, and stability.

Researchers should be followed up until the end of AE, stable status, reasonable explanation, loss to follow-up, or death; Follow up information should be provided promptly according to the requirements of the sponsor.

If there are no specific requirements in the protocol, AE/SAE collection and follow-up usually begin after the subjects sign the informed consent form, and each AE/SAE must be followed up during the study period; At the end of the study, the collection and follow-up principles for AE/SAE that occurred after the final treatment of the subjects can refer to the following table:

- Various adverse events: Take timely measures to handle them and record them in the case report form. Serious Adverse Events (SAEs): Take timely measures to handle them, record them in the case report form, have the researcher decide to discontinue or reduce the drug, immediately report to the ethics committee, drug clinical trial institution, and sponsor, and report to the national and provincial food and drug regulatory authorities within 24 hours

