2.2 Secondary research objectives

2.2.1 Evaluate the impact of intensified adjuvant therapy on 1-year and 2-year overall survival rates and quality of life in patients with newly diagnosed glioblastoma who undergo partial surgical resection or short-term recurrence progression.

2.2.2 Evaluate the safety and incidence of radiation necrosis in newly diagnosed glioblastoma patients undergoing enhanced adjuvant therapy with surgical partial resection or short-term recurrence progression.

3, Research design and methodology:

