Stupp+PD-1/CTLA-4 dual antibody group: Starting 2-6 weeks after surgery, synchronous TMZ radiotherapy and chemotherapy will be performed. After completing synchronous radiotherapy and chemotherapy for 28 days, TMZ combined with PD-1/CTLA-4 dual antibody will be used as adjuvant therapy. PD-1/CTLA-4 dual antibody 6mg/kg intravenous infusion once, with a cycle of 14 days.

Modified Stupp group: Starting 2-6 weeks after surgery, synchronous TMZ radiotherapy and chemotherapy will be performed. For partially resected lesions or short-term recurrence and progression lesions after surgery, high-dose PGT 66Gy/30Gy will be given locally. PTV1 in high-risk areas around the tumor bed will be 60Gy/30F, and in low-risk areas will be 54Gy/30F. After completing synchronous radiotherapy and chemotherapy for 28 days, 6 cycles of adjuvant TMZ chemotherapy will be started.

This study is divided into three stages: screening period, treatment period, and follow-up period. The screening period is 2-6 weeks after surgery. Treatment period: Subjects who meet the inclusion criteria but do not meet the exclusion criteria will receive postoperative intensive adjuvant therapy after signing the informed consent form. Follow up period: After stopping the study treatment, the subjects enter the follow-up period. Follow up period: Head MRI examination and evaluation will be conducted at baseline, postoperative, before radiotherapy, and after radiotherapy. MRI enhanced scans will be performed every month during the follow-up period to observe PFS until the end of the follow-up period. For subjects who have not withdrawn their informed consent form, survival information (i.e. date and cause of death, subsequent tumor treatment, etc.) will be collected every month through telephone and/or clinical visits.

This study is expected to have an enrollment period of 24 months and a follow-up period of 24 months.

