7.1 Definition

AE refers to any adverse medical event that occurs from the signing of the informed consent form by clinical trial subjects until 90 days after the last use of the study treatment, regardless of whether there is a causal relationship with the trial treatment, and is determined as an adverse event.

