7.5 Criteria for determining the relationship between adverse events and investigational drugs

AE includes all unexpected clinical manifestations, as long as these events occur after signing the informed consent form, regardless of whether they are related to the experimental treatment, they should be reported as AE. During the treatment period, any discomfort or abnormal changes in objective laboratory test indicators reported by the subject should be recorded truthfully, and the severity, duration, treatment measures, and outcome of the AE should be indicated. The research physician should also comprehensively determine the relationship between the AE and the investigational drug, and evaluate the possible association between the AE and the investigational treatment according to the five level classification system of "definitely related, possibly related, possibly unrelated, definitely unrelated, and unable to determine" Definitely related "," possibly related ", and" unable to determine "are all listed as adverse drug reactions, and the determination criteria are shown in the following table:

Table 1 Criteria for Judging the Relationship between AE and Experimental Treatment

Grading criteria

Definitely related: the occurrence of the event conforms to a reasonable chronological order after treatment, and the event conforms to the known reaction type of the suspected drug;

Alternatively, if the condition improves after discontinuing the medication and the event occurs again after repeated administration.

Possible correlation: The occurrence of events follows a reasonable chronological order after treatment, and the events do not conform to the known reaction type of the suspected drug; The patient's clinical condition or other treatment methods may also cause this event.

Possible unrelated: The occurrence of the event does not conform to a reasonable chronological order after treatment, the event does not conform to the known response type of the suspected drug, and the patient's clinical status or other treatment methods may have caused the event.

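### Radiation necrosis is a secondary objective, but adverse-event collection closes 90 days after last treatment and later SAEs depend on a drug-attribution rule, so late necrosis can be under-counted in all arms

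*Protocol*

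**What the plan says.** Four parts of the protocol bear on this.

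- **Objective.** Section 2.2.2 sets out to "Evaluate the safety and incidence of radiation necrosis in newly diagnosed glioblastoma patients" given the intensified therapy.
- **Treatment under test.** In section 3.1 the modified Stupp arm adds no drug to the Stupp regimen. Its experimental element is that "high-dose PGT 66Gy/30Gy will be given locally" to residual or early recurrent lesions. (The unit notation in that phrase needs its own check; nothing here depends on it.)
- **Collection window.** Section 7.1 defines an adverse event as one occurring from consent "until 90 days after the last use of the study treatment". Section 7.6 item 3 has adverse-event records "continue until 90 days after the last use of the study drug", and item 5 has SAE reporting "continue until 90 calendar days (including 90 days) after the last use of the study drug". One anchor is treatment and the other is drug. *Study drug* is not defined by arm.
- **After the window.** Section 7.6 says a later SAE "is generally not reported unless suspected to be related to the study drug". The highest causality category in section 7.5 asks whether "the event conforms to the known reaction type of the suspected drug", and no category is written for radiotherapy.

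Imaging does continue: section 3.1 states that "MRI enhanced scans will be performed every month during the follow-up period", but the purpose it gives is observation of PFS. The protocol gives no definition, schedule or collection rule for radiation necrosis itself.

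**The concern.** The collection rule does not fit the objective. A harm of radiotherapy is to be counted, but the clock that closes collection runs from the last dose of drug or treatment, and the only route back in after closure is suspected causation by a drug. A non-serious necrosis seen after the window is not collected as an adverse event. A serious one is reported only if someone is prepared to suspect the drug, which is least natural in the arm whose experimental component is radiation.

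At stake is whether the trial can answer objective 2.2.2 beyond the first months after radiotherapy. An incomplete count would make radiotherapy-related harm look smaller than it is, and the SAP cannot repair this, because it cannot analyse events that were never recorded. A further worry is that closure follows each patient's actual treatment duration, so arms with different exposure could be watched for different lengths of time.

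**Working it through.** The protocol states no figure for this window, so there is none to reproduce. The check is calendar arithmetic, counted in days from the end of radiotherapy.

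**Inputs.** Section 3.1: a 28-day gap between chemoradiotherapy and adjuvant treatment; 28-day temozolomide cycles with dosing on days 1 to 5; six cycles in the Stupp and modified Stupp arms; antibody cycles of 21 days (PD-1/VEGF) and 14 days (PD-1/CTLA-4) with no number of cycles stated; 24 months of follow-up. Sections 7.1 and 7.6: 90 days. One month is taken as 30.4375 days. Temozolomide is taken to count as study drug.

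**Stupp and modified Stupp.** Last dose after *c* cycles = 28 + 28(*c* − 1) + 4; closure = last dose + 90.

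| Adjuvant cycles | Last dose (day) | Closure (day) | Months |
|---|---|---|---|
| 6 | 28 + 140 + 4 = 172 | 262 | 8.6 |
| 3 | 28 + 56 + 4 = 88 | 178 | 5.8 |
| 2 | 28 + 28 + 4 = 60 | 150 | 4.9 |
| 0 | 0 (last concurrent dose assumed at the end of radiotherapy) | 90 | 3.0 |

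Both arms have the same planned schedule after radiotherapy, so the planned window is identical.

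**Share of follow-up.** If the 24 months are counted from the end of radiotherapy, the six-cycle window covers 262 / 730.5 = 36%. Section 3.1 starts the follow-up period when study treatment stops. On that count the window covers only 90 / 730.5 = 12% of it. These are shares of calendar time, not of necrosis cases.

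**Antibody arms.** The duration must be assumed. Closure = 28 + day of last infusion counted from the first + 90.

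| Assumed duration | 21-day cycle | 14-day cycle |
|---|---|---|
| About 6 months | 28 + 147 + 90 = 265 (8.7 months) | 28 + 154 + 90 = 272 (8.9 months) |
| 12 months | 28 + 357 + 90 = 475 (15.6 months) | 28 + 364 + 90 = 482 (15.8 months) |
| 24 months | 28 + 714 + 90 = 832 (27.3 months) | 28 + 728 + 90 = 846 (27.8 months) |

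The antibody windows are therefore practically equal to the six-cycle window, or much longer, depending on a duration the protocol does not give.

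**What lies outside the window.** Setting sections 7.1, 7.5 and 7.6 side by side: non-serious necrosis after closure has no collection route; serious necrosis after closure has one only through suspected relation to a drug; the monthly MRI could show either, but nothing directs that it be recorded.

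**The case against.** The best defence has five parts.

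1. **The drug test is not as narrow as it looks.** The possibly-related category in section 7.5 admits a plausibly timed event that does not fit the drug's known reactions and that another treatment might also explain. All arms give temozolomide with radiotherapy, so some late necrosis SAEs could qualify, and the late-SAE sentence is hedged with *generally*. This stands in part. It makes capture discretionary in an open-label trial, and it does nothing for non-serious necrosis.
2. **SAE reporting is not the same as measuring an objective.** Monthly MRI continues in every arm. This also stands in part: the images will exist, but their stated purpose is PFS. For patients who withdraw for reasons other than progression, section 3.3.4 ends imaging at progression or new anti-tumour treatment.
3. **Section 7.6 item 6 points to a table on events after final treatment.** Its body cannot be read in the text available for review, so it might add something. However, it is introduced as applying where the protocol has no specific requirement, and the 90-day rule is one.
4. **The method of analysis belongs in the SAP.** Agreed. The point here is the collection rule.
5. **Unequal cut-off is not established.** A reader might infer that necrosis is cut off unequally by arm. The documents do not support that as a fact. The comparison that isolates the radiotherapy boost, modified Stupp against Stupp, has equal planned windows, and any difference from the antibody arms rests on an unstated duration. This objection stands in full.

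**Conclusion.** The point holds as a mismatch between an objective and the rules for collecting data on it. Followed as written, the protocol can under-count radiation necrosis in all four arms once collection closes. For the Stupp and modified Stupp arms that is about 8.6 months after radiotherapy with six cycles completed, and about 3.0 to 5.8 months with none to three.

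Two stronger readings should be resisted. Not all late necrosis is excluded, since attribution and discretion may let some SAEs through and scans continue. Bias between arms has also not been demonstrated: windows follow actual treatment duration and so can differ if exposure differs, but that is a risk only.

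The conclusion assumes that temozolomide counts as study drug and that some necrosis arises after the window closes. The documents give no onset distribution, so the number of cases missed cannot be calculated. Deaths would also limit it: section 1.2 puts median overall survival at about 15 to 18 months.

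**What to change.** Reconcile sections 2.2.2, 3.1, 7.1 and 7.6, and in doing so:

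- State that radiation necrosis, with date and grade, is recorded in all four arms from the monthly MRI already planned. The period should be the same in every arm, from the start of radiotherapy to the end of follow-up or death, regardless of the 90-day window and of attributed cause.
- Use one anchor for the 90-day window throughout, and in the late-SAE rule replace *study drug* with *study treatment, including radiotherapy*.
- Say how necrosis is followed in patients whose imaging ends early under section 3.3.4.
- Report necrosis as cumulative incidence from the start of radiotherapy with death as a competing event. The detail can sit in the SAP.

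The cost is one extra CRF field read from scans already scheduled, a few more late SAE reports, and the rewording. No additional visits or scans are needed for this.
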